11.5. Expedited Reporting Guidelines

The following adverse events require expedited reporting:

- All adverse events that are both serious and unexpected regardless of grade
- Adverse events that might influence the benefit-risk assessment of administration of poly-ICLC as outlined in the protocol
- All grade 5 adverse events
- A serious adverse event that occurs within 30 days of the last dose of the investigational agent
- Pregnancy

If a participant or a participant's partner becomes pregnant while receiving investigational therapy or within 30 days after the last dose of study drug, a report should be completed and expeditiously submitted as an SAE. Follow-up to obtain the outcome of the pregnancy should also occur. Abortion, whether accidental, therapeutic, or spontaneous, should always be classified as serious, and expeditiously reported as an SAE. Similarly, any congenital anomaly/birth defect in a child born to a female participant exposed to the poly-ICLC should be reported as an SAE.

- Expedited AE reporting timelines defined:

"24 hours; 3 business days" – The investigator must initially report the AE within 24 hours (or immediately if the event is fatal or life-threatening) of learning of the event to the Study Chair ([contact]) and NF Operations Center, followed by a complete written report within 3 business days of the initial 24-hour report.

Adverse events requiring expedited reporting will be reported and documented on **Form FDA 3500A MedWatch Form** <http://www.fda.gov/medwatch/getforms.htm>) and forwarded to:

NFCTC Operations Center

Clinical Research Manager: [name], BS

Program Director: [name], BS

Research Compliance Manager: [name], BS, CCRP

Direct Email: [contact]

The clinical research manager from the NFCTC Operations Center will forward all related adverse events that are both serious and unexpected to the FDA on **Form FDA 3500A MedWatch Form** <https://www.fda.gov/media/69876/download>:

MedWatch
Fax: [name]

The final MedWatch Form or CIOMS-1 form will be submitted by the Clinical Research Manager to Oncovir within one to two business days of submission to the FDA or applicable regulatory agency (including confirmation of date that the report was submitted) to allow Oncovir time to cross-report to Oncovir's IND. E-mail: [contact]; [contact].

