 - e. Growth factor(s): Must not have received any hematopoietic growth factors within 7 days of study entry or $>$ 14 days if pegylated GCSF is used.
 - f. Prior surgery: At the time of enrollment, must be \geq 3 weeks from prior major surgery such as craniotomy, orthopedic surgery, abdominal surgery or \geq 1 week from minor surgery

and completely recovered. Port or central line placement is not considered a major surgery.

9) Organ Function Requirements:

All patients must have adequate organ function defined as:

9.1 Hematologic Function:

- a. Hemoglobin: ≥ 8.0 gm/dL (may transfuse PRBCs)
- b. ANC: $\geq 750/\text{mm}^3$. Must be at least 7 days after last dose of growth factor or > 14 days since last dose of pegylated GCSF
- c. Platelet Count: $\geq 75,000/\text{mm}^3$ (transfusion independent; ≥ 7 days from last transfusion)

9.2 Renal Function: Serum creatinine which is less than 1.5 times ULN for age (as per the table below) or GFR > 70 ml/min/1.73m²

Table 3: Renal Function Normal for Age

Age	Maximum Serum Creatinine (mg/dL)	
	Male	Female
1 month to < 6 months	0.4	0.4
6 months to < 1 year	0.5	0.5
1 to < 2 years	0.6	0.6
2 to < 6 years	0.8	0.8
6 to < 10 years	1	1
10 to < 13 years	1.2	1.2
13 to < 16 years	1.5	1.4
≥ 16 years	1.7	1.4

9.3 Liver Function:

- a. Total bilirubin $\leq 1.5 \times$ ULN (Children with diagnosis of Gilbert's Syndrome will be allowed on the study regardless of their total and indirect bilirubin levels as long as the direct bilirubin is less than 3.1 mg/dL.)
- b. SGPT (ALT) $\leq 5 \times$ ULN
- c. SGOT (AST) $\leq 5 \times$ ULN

9.4 Pulmonary Function:

No evidence of dyspnea at rest, and a pulse oximetry $\geq 92\%$.

9.5 Reproductive Function:

Female patients of childbearing potential must have a negative serum or urine pregnancy test within 7 days prior to the first dose of poly-ICLC. Patient must not be pregnant or breast-feeding. Patients of childbearing or child-fathering potential must be willing to use a medically acceptable form of birth control, including abstinence, while being treated on this study and for 90 days following cessation of treatment.

- 10) Patient is able to start treatment within 7 days after enrollment.
- 11) Patients with neurological deficits must be stable for a minimum of 1 week prior to enrollment.
- 12) Patients are only eligible if complete resection of the LGG with acceptable morbidity is not feasible or if a patient with a surgical option refuses surgery.

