3.2. Exclusion Criteria

1. Prior radiation treatment for the low-grade glioma.
2. Prior exposure to poly-ICLC.
3. Patients currently receiving other anti-tumor therapy or experimental therapy (targeted agents, chemotherapy radiation).
4. Patients with a current or prior diagnosis of malignant glioma (WHO grade III or IV).
5. Patients with a prior diagnosis of malignant peripheral nerve sheath tumor or other malignancy requiring treatment in the last 48 months.
6. Patients may not have fever (≥ 38.50 C) within 3 days of enrollment.
7. Patients who, in the opinion of the investigator, may not be able to comply with the safety monitoring requirements of the study.
8. Active auto-immune illness.
9. Pregnant or lactating females.
10. Sexually active patients of reproductive potential who have not agreed to use an effective contraceptive method for the duration of their study participation and for 90 days after stopping study therapy are not eligible.
11. Severe unresolved infection that requires systemic IV antibiotics.
12. Patients with any significant medical illnesses that in the investigator's opinion cannot be adequately controlled with appropriate therapy or would compromise the patient's ability to tolerate this therapy.
13. Uncontrolled intercurrent illness including, but not limited to, ongoing or active infection, symptomatic congestive heart failure, unstable angina pectoris, cardiac arrhythmia, impaired gastrointestinal function, or psychiatric illness/social situations that would limit compliance with study requirements.
14. Patients requiring high doses of steroids. Patients may not be on immunosuppressive therapy, including corticosteroids (with the exception of physiologic replacement, defined as ≤ 0.75

mg/m²/day dexamethasone or equivalent) at time of enrollment. However, patients who require intermittent use of bronchodilators or local steroid injections will not be excluded from the study.

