3.5. Criteria for Removal from Protocol Therapy and Off Study Criteria

Removal from Protocol Therapy

The following are criteria for removal from protocol therapy:

- a) Confirmed progressive disease (clinical or radiographic).
- b) Completion of cycle 24.
- c) Poly-ICLC related toxicity requiring removal.
- d) Participant has not received drug (for any reason) for greater than 28 days.
- e) Refusal of further protocol therapy by participant/parent/guardian.
- f) Another tumor develops that requires non-surgical therapy (e.g. chemotherapy, radiation etc;).
- g) Non-compliance, that in the opinion of the investigator does not allow for on-going participation.
- h) Physician determines it is not in the participant's best interest.
- i) Participant has complete resection of target lesion and there is no evidence of residual disease.
- j) Participant becomes pregnant.
 - If a participant becomes pregnant while receiving investigational therapy or within 90 days after the last dose of study drug, the participant should be followed until the outcome of the pregnancy.

Participants who are off protocol therapy are to be followed until they meet the criteria for OFF Study (see below).

Off-Study Criteria:

- Completion of their 5 year follow-up MRI scan
- Participant starts new tumor-directed therapy
- Death
- Lost to follow-up
- Withdrawal of consent for any further data submission

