11. ADVERSE REPORTING REQUIREMENTS

11.1. Definitions

Adverse Events: An adverse event is any new, undesirable medical occurrence or change (worsening) of an existing condition in a participant that occurs from study enrollment until 30 days after drug discontinuation, whether or not considered to be product related. Therefore, adverse events are treatment emergent signs or symptoms. Elective hospitalizations for pretreatment conditions (e.g., elective cosmetic procedures) are not adverse events. Non-clinically significant abnormal laboratory values should not be reported as adverse events; however, any clinical consequences of the abnormality should be reported as adverse events. All adverse events must be noted on the electronic case report forms and submitted via eDCS within 2 weeks of completion of every treatment cycle.

For all adverse events, the investigator must pursue and obtain information adequate both to determine the outcome of the adverse event and to assess whether it meets the criteria for classification as a serious adverse event requiring immediate notification (within 24 hours) to the site PI and clinical coordinator, as well as the NFCTC Operations Center. Follow-up of the adverse event, even after the date of therapy discontinuation, is required if the adverse event or its sequelae persist. Follow-up is required until the event or its sequelae resolve or stabilize at a level acceptable to the investigator and sponsor.

Serious Adverse Events: A serious adverse event is defined by regulatory agencies as one that suggests a significant hazard or side effect, regardless of the investigator's or sponsor's opinion on the relationship to investigational product.

This includes, but may not be limited to, any event that (at any dose):
is FATAL;
is LIFE THREATENING (places the participant at immediate risk of death);
requires HOSPITALIZATION or prolongation of existing hospitalization;
is a persistent or significant DISABILITY/INCAPACITY; or
is a CONGENITAL ANOMALY/BIRTH DEFECT

Important medical events that may not be immediately life threatening or result in death or hospitalization but may jeopardize the participant or require intervention to prevent one of the outcomes listed above, or result in urgent investigation, may be considered serious. Examples include allergic bronchospasm, convulsions, and blood dyscrasias.

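### Section 11.5 limits pregnancy reporting and outcome follow-up to 30 days after the last dose, while the protocol's contraception and participant follow-up rules run to 90 days

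*Combined protocol and SAP*

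**What the plan says.** **Reporting (section 11.5).** Pregnancy is one of the listed expedited events, and the list entry has no time limit. The paragraph below it does: a pregnancy in a participant or partner is covered if it arises on therapy or "within 30 days after the last dose of study drug, a report should be completed and expeditiously submitted as an SAE". The next sentence adds "Follow-up to obtain the outcome of the pregnancy should also occur". Expedited reporting means notice within 24 hours, then a full written report within 3 business days.

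**Contraception (sections 3.1 and 3.2).** Patients of childbearing or child-fathering potential must use birth control "while being treated on this study and for 90 days following cessation of treatment". The matching exclusion criterion requires agreement to contraception "for the duration of their study participation and for 90 days after stopping study therapy".

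**Follow-up (section 3.5, item j).** If a participant becomes pregnant on therapy or "within 90 days after the last dose of study drug, the participant should be followed until the outcome of the pregnancy". Partners are not mentioned.

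**Pregnancy outcomes (section 11.5).** Two further sentences have no time limit: "Abortion, whether accidental, therapeutic, or spontaneous, should always be classified as serious, and expeditiously reported as an SAE", and "any congenital anomaly/birth defect in a child born to a female participant exposed to the poly-ICLC should be reported as an SAE".

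**General adverse events (section 11.1).** An adverse event is a new occurrence or a "change (worsening) of an existing condition in a participant that occurs from study enrollment until 30 days after drug discontinuation".

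**The concern.** Sections 3.5 and 11.5 describe the same situation in nearly the same sentence, one with 90 days and the other with 30. The protocol gives no reason for the difference. By asking for contraception through day 90, it treats days 31 to 90 as a period in which a pregnancy matters, yet its reporting rule stops at day 30.

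Two things are at stake. For a participant's pregnancy in that interval, sites may disagree on whether the rapid notice to the study chair and operations center is due. For a partner's pregnancy, the text does not require the sponsor to learn of it or of how it ended, even though the male participant is bound to contraception over the same days. The documents contain no reproductive data for this window, so the point is consistency of safety reporting and not evidence of harm.

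**Working it through.** The plan states no figure to reproduce. The check compares the windows, works through each case, and then bounds the size.

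**1. Windows after the last dose**

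| Rule | Section | Who | Days |
|---|---|---|---|
| Contraception | 3.1 (item 9.5) | Patients of childbearing or child-fathering potential | 90 |
| Contraception | 3.2 (item 10) | Sexually active patients of reproductive potential | 90 |
| Pregnancy follow-up to outcome | 3.5 (item j) | Participant only | 90 |
| Expedited pregnancy report, with follow-up | 11.5 | Participant or partner | 30 |
| General adverse events | 11.1 | Participant | 30 |

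Gap: 90 − 30 = 60 days, that is, days 31 to 90.

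**2. What applies on days 31 to 90**

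- *Participant's pregnancy.* Section 3.5 requires follow-up to outcome. The expedited report depends on whether the untimed list entry or the 30-day paragraph in section 11.5 governs. Section 11.6 (deviations and unanticipated problems) and section 13.4 (data submission after required evaluations while on study) might bring the event in, but neither names pregnancy or sets the 24-hour and 3-business-day timeline.
- *Partner's pregnancy.* Section 3.5 does not cover partners, and the paragraph in section 11.5 has ended. No express rule requires a report or follow-up.
- *Abortion.* Reportable if known, since that sentence is not limited by time or to participants. A partner's abortion may not become known if nobody has to report or follow the pregnancy.
- *Birth defect.* Reportable for a female participant's child without a time limit. A child fathered by a male participant is not named, whatever the timing. Section 11.1 lists congenital anomaly among serious events, but defines an adverse event as occurring in a participant up to 30 days after discontinuation.

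**3. Size**

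- Maximum enrollment, section 14.2: 20 patients.
- Upper bound on exposure: 20 × 60 = 1,200 patient-days; 1,200 / 365.25 = 3.29 patient-years.
- Pregnancy rate: not in the documents. Assumed range: 1 to 10 per 100 patient-years.
- Expected cases = patient-years × rate: 3.29 × 0.01 = 0.03, and 3.29 × 0.10 = 0.33.
- Poisson probability of no case, exp(−expected): exp(−0.03) = 0.97, and exp(−0.33) = 0.72.

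The bound is generous. It counts every patient as of reproductive potential and under follow-up for the full 60 days. Section 3.1 sets no lower age limit, so some patients will be too young. Under section 3.5, a patient who starts new tumor-directed therapy goes off study.

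**The case against.** The strongest reply is that this is an ambiguity of little consequence. The list entry in section 11.5 has no window, so a site could read it as the rule and the paragraph as detail. For female participants, section 3.5 already secures the outcome, and abortions and birth defects are reportable without a time limit, so only the speed of the first notice is in doubt. Section 11.6 calls for prompt reporting of safety-relevant unanticipated problems, and the operations center's duty extends to risks to persons other than participants. A precautionary contraception period need not equal a reporting period, and 30 days matches the general adverse event window. The off-therapy calendar (Appendix 4) has no pregnancy test, so a longer window would still depend on families volunteering the information. The expected number of cases is well below one.

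Much of this is fair, and it limits the point without removing it:

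- If the list entry were unlimited, the 30 days in the next paragraph would have no effect. At best the section can be read in two ways.
- Section 11.6 does not name pregnancy, and contraception can fail without any deviation from the protocol.
- The match with section 11.1 may explain where the 30 days came from, but section 3.5 sets 90 days for pregnancy itself.
- None of the mitigations supplies an express rule for a partner's pregnancy on days 31 to 90.
- The extension of the birth-defect sentence is a separate improvement, because that sentence has no 30-day limit to correct.

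**Conclusion.** The concern holds. The reporting window in section 11.5 is 60 days shorter than the protocol's own contraception window and its follow-up window for participant pregnancies. The substantive gap is the partner's pregnancy. For the participant's pregnancy, the defect is an unclear duty to give rapid notice.

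The practical size is small: no case is the most likely result, even under the generous bound and the assumed rates. The primary endpoint, the sample size and the efficacy analyses are untouched. This should be corrected as a limited safety-reporting inconsistency.

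The conclusion concerns the protocol text only. The Multi-Center Data and Safety Monitoring Plan named in section 13.7 and the consent pages were not available, and either could contain pregnancy-reporting instructions.

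**What to change.** Amend section 11.5 as follows:

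1. Replace 30 days with 90 days in the pregnancy paragraph, for participants and partners alike.
2. State that follow-up to the outcome of the pregnancy applies to both.
3. As a separable addition, extend the birth-defect sentence to cover a child fathered by a male participant.

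Leave the 30-day window for all other adverse events as it is.

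The cost is two or three sentences in an IRB-approved amendment, which can go with the next one, and at most a few extra reports. Endpoints, sample size and analyses do not change.

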11.6. Reporting of Protocol Violations/Deviations and Unanticipated Problems

Site reporting to NFCTC Operations Center

Sites will report unanticipated problems and/or protocol deviations that impact participant safety or the scientific integrity of the study to the Operations Center promptly to [contact] and entered into eDCS. Other protocol violations and deviations should be reported to the NF Operations Center in eDCS within 14 days of the visit.

NFCTC Operations Center reporting requirements

The Operations Center will report unanticipated problems that impact participant safety or the scientific integrity of the study to the USAMRMC Office of Human and Animal Research Oversight (OHARO) OHRO promptly. Unanticipated problems will also be reported to the protocol team, Research Monitor, and DSMB.

All unanticipated problems involving risk to participants or others must be promptly reported by the NFCTC Operations Center via [contact]), email ([contact]), or [contact]) to the OHRO. A complete written report will follow the initial notification. In addition to the methods above, the complete report can be sent to the US Army Medical Research and Materiel Command, ATTN: MCMR-RP, [name], Fort Detrick, Maryland 21702-5000.

Suspensions, clinical holds (voluntary or involuntary), or terminations of this research by the IRB, the institution, the Sponsor, or regulatory agencies will be promptly reported to the USAMRMC OHARO OHRO.

Other protocol violations and deviations that do not impact participant safety or affect scientific integrity of the study will be provided annually to the Sponsor.

12. RESEARCH MONITORING AND DATA SAFETY MONITORING PLAN

The trial PI and clinical coordinator will review the study progress regularly. Participants entered on the trial and adverse events will be reviewed to ensure that the study is implemented as outlined in the protocol. Monthly reports will be generated by the NFCTC to assess completeness of data. There will be monthly phone conferences between the NFCTC and the Principal Investigator to address QA issues. A Data Safety Monitoring Board has been established for the purpose of ensuring data compliance and regular monitoring of this trial.

Additionally, there will be a designated research monitor for this study. This person is a qualified physician and is not associated with this particular protocol. The designated research monitor will work closely with the Principal Investigator to monitor the participants' treatment while on this study.

The research monitor's duties should be based on specific risks or concerns about the research. The research monitor may perform oversight functions and report their observations and findings to the IRB or a designated official. The research monitor may be identified from within or outside the PI's institution.

Research monitor functions may include:

- observing recruitment and enrollment procedures and the consent process for individuals, groups or units,
- overseeing study interventions and interactions,
- reviewing monitoring plans and UPIRTSO reports;
- overseeing data matching, data collection, and analysis

There may be more than one research monitor (e.g., if different skills or experiences are necessary). The monitor may be an ombudsman or a member of the data safety monitoring board.

At a minimum, the research monitor:

- may discuss the research protocol with the investigators, interview human participants, and consult with others outside of the study about the research;
- shall have authority to stop a research protocol in progress, remove individual human participants from a research protocol, and take whatever steps are necessary to protect the safety and well-being of human participants until the IRB can assess the monitor's report;
- shall have the responsibility to promptly report their observations and findings to the IRB or other designated official and the OHRO.

In addition, on this study, the research monitor is specifically required to review all unanticipated problems involving risk to participants or others, serious adverse events and all participant deaths associated with the protocol and provide an unbiased written report of the event. At a minimum, the research monitor should comment on the outcomes of the event or problem, and in the case of a serious adverse event or death, comment on the relationship to participation in the study. The research monitor should also indicate whether he/she concurs with the details of the report provided by the study investigator.

Safety Monitoring Criteria

Table 14 below defines the maximum allowed number of Grade 4 adverse events that are at least possibly attributable to the study drug.

If the number of events exceeds the number in the second column, accrual to the study should be placed on hold for safety evaluation, pending review of toxicities by the study committee in consultation with the DSMB and the research monitor, to determine whether the study should continue, be amended, or be terminated. For example, if 2 or more patients experience an event before the sixth patient begins therapy, the trial will be on hold.

Table 14. Safety Rules for Grade 4 Adverse Events

Number of Patients	Maximum Number Permitted	Probability to Stop	Cumulative Probability to Stop
5	1	0.081	0.081
10	2	0.070	0.151
16	3	0.068	0.219

Statistical Justification: The trial should hold enrollment and have a DSMB evaluation for safety if the probability that a Grade 4 adverse event (defined above) exceeds 10% is equal to or higher than 0.95, i.e., stop if $\Pr\{\Theta > 0.10 | \text{data}\} \geq 0.95$. The table above gives the safety rule for each set of 5 participants that enrolls in the study, with column 2 indicating the maximum number of cases of events that are permitted. The third column gives the probability of holding enrollment on the trial when in fact, the true $\Theta = 0.10$. Safety rules were generated using a binomial distribution.

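### The only numeric accrual-hold rule counts Grade 4 events alone, so a drug-related event recorded only as Grade 5 does not move it

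*Combined protocol and SAP*

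**What the plan says.** Section 12, under Safety Monitoring Criteria, names the counted event three times.

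- Lead sentence: "Table 14 below defines the maximum allowed number of Grade 4 adverse events that are at least possibly attributable to the study drug".
- Table title: "Table 14. Safety Rules for Grade 4 Adverse Events".
- Statistical justification: enrollment is held "if the probability that a Grade 4 adverse event (defined above) exceeds 10% is equal to or higher than 0.95".

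None of the three says 'or higher' or 'Grade 4-5'.

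The consequence of crossing a limit is stated as "If the number of events exceeds the number in the second column, accrual to the study should be placed on hold for safety evaluation". The study committee then reviews with the DSMB and the research monitor. The worked example counts patients: "if 2 or more patients experience an event before the sixth patient begins therapy, the trial will be on hold". The limits are 1, 2 and 3 at 5, 10 and 16 patients.

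Elsewhere the plan treats Grade 5 as its own category. Section 11.5 lists "All grade 5 adverse events" among the events needing expedited reporting. Section 12 also obliges the research monitor to review every death associated with the protocol, and gives that monitor authority to stop the study. Section 14.3 adds only that toxicity is monitored continuously, with no threshold.

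**The concern.** A hold rule should never become less likely to fire when an outcome gets worse. As worded, this one can. If a patient's related event is recorded as Grade 5 rather than Grade 4, the count falls by one.

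The rule exists to pause accrual when the rate of severe drug-related toxicity is probably above 10%. Leaving out fatal events understates that rate. Accrual of children and young adults could then continue without the automatic pause, in data where counting the worse event would have met the plan's own criterion.

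**Working it through.** **Inputs.** From section 12: looks at 5, 10 and 16 patients; limits 1, 2 and 3; hold when the limit is exceeded; true rate Θ = 0.10; binomial distribution; posterior threshold 0.95. The documents give no prior and no Grade 5 rate, so anything that needs these is marked as an assumption.

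**1. Reproduce the plan's per-look probabilities.** P(X ≥ limit + 1) for X ~ Bin(n, 0.10):

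- n = 5: 1 − 0.9⁵ − 5(0.1)(0.9⁴) = 1 − 0.5905 − 0.3281 = 0.0815 (table: 0.081)
- n = 10: P(X ≥ 3) = 0.0702 (table: 0.070)
- n = 16: P(X ≥ 4) = 0.0684 (table: 0.068)

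The third column is confirmed.

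**2. Check the limits against the stated criterion.** Under a uniform prior (assumption), Pr(Θ > 0.10 | data) is:

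| Patients | At the limit | One above the limit |
|---|---|---|
| 5 | 0.886 (1 event) | 0.984 (2 events) |
| 10 | 0.910 (2 events) | 0.981 (3 events) |
| 16 | 0.917 (3 events) | 0.978 (4 events) |

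This prior reproduces all three limits, so two qualifying patients among 5 do meet the plan's criterion.

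**3. Apply the rule literally to the first 5 patients (limit 1).** All events are at least possibly related and occur in different patients.

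| Events | Count as written | Hold? | Count if Grade 4 or 5 | Hold? |
|---|---|---|---|---|
| Two Grade 5 | 0 | No | 2 | Yes |
| One Grade 5, one Grade 4 | 1 | No | 2 | Yes |
| Two Grade 4 | 2 | Yes | 2 | Yes |
| One Grade 5 | 0 | No | 1 | No |

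**4. Effect of widening the count.** The overall hold probability needs a sequential calculation that carries forward only the paths not yet held. At Θ = 0.10:

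- Look 1: 0.0815.
- Look 2: from 0 events, 0.5905 × P(≥3 of 5) = 0.5905 × 0.0086 = 0.0051; from 1 event, 0.3281 × P(≥2 of 5) = 0.3281 × 0.0815 = 0.0267; sum 0.0318.
- Look 3, by the same recursion: 0.0238.
- Total: 0.0815 + 0.0318 + 0.0238 = 0.137.

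The table's cumulative 0.219 is the plain sum 0.081 + 0.070 + 0.068. It counts some paths more than once. That is a separate matter and does not affect this point.

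Now keep a Grade 4 rate of 10% and add an assumed Grade 5-only rate, counting each patient once:

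| Assumed Grade 5 rate | Combined rate | Overall hold probability by patient 16 |
|---|---|---|
| 0 | 10% | 0.137 |
| 1% | 11% | 0.167 |
| 2% | 12% | 0.199 |
| 5% | 15% | 0.307 |

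Under the present wording the figure stays at 0.137 in every row.

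**5. What widening does not do.** Suppose only Grade 5 events occur, at an assumed 5%. The chance of at least one death in 16 patients is 1 − 0.95¹⁶ = 0.56. With deaths counted under limits 1, 2 and 3, the chance of a hold is only 0.031.

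**The case against.** The strongest reply is that a reader might infer that deaths escape control in this trial, and the documents do not support that. Section 11.5 requires fatal events to be reported immediately. Section 12 makes the research monitor's review of each death mandatory, with a written report and a comment on relationship. The monitor may stop the study and must report findings promptly to the IRB or another designated official and to OHRO. Section 11.6 sends unanticipated problems to the DSMB. Independent review therefore starts at the first death, and a Table 14 hold would itself end in judgement. All of this stands. It leaves one gap: none of these routes sets a count at which accrual must pause.

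It is also tempting to say that a trivial laboratory value outranks a death. Sections 11.1 and 11.4 exclude laboratory findings that are not clinically significant, so the fair comparison is with a reportable Grade 4 event. And because the worked example counts patients, two such events in one patient would not be enough under that reading.

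Three further limits hold. A patient whose related Grade 4 event was recorded before death would already be counted. The authors may have meant Grade 4 or higher, though no sentence says so. Section 13.7 refers to a separate Multi-Center Data and Safety Monitoring Plan that is not among the documents and might address deaths.

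Finally, adding deaths to a column of permitted numbers sits awkwardly, and a single death would still pass. That is a fair criticism of relying on the edit alone.

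**Conclusion.** The point holds for the accrual-hold rule as written. Events recorded only as Grade 5 contribute nothing, so in the first 5 patients two related deaths, or one related death plus one other patient with a Grade 4 event, produce no automatic hold, while two patients with Grade 4 events do.

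The conclusion rests on the literal text of section 12 and on Grade 5 being a separate grade, as section 11.5 treats it. It does not depend on any assumed death rate. It is a gap in one automatic trigger, not an absence of safety oversight, and the primary efficacy analysis is unaffected. It should be fixed, but it is not a flaw that undermines the trial.

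The documents give no Grade 5 rate, so no probability can be put on the gap mattering in practice. The combined rates of 11% to 15% show a range only.

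**What to change.** In section 12, replace 'Grade 4' with 'Grade 4 or 5' in the lead sentence, the Table 14 title and the statistical justification. State that the count is of patients with at least one such event, and define Θ as the combined Grade 4-5 rate. With the 10% threshold kept, the limits 1, 2 and 3 and the per-look probabilities 0.081, 0.070 and 0.068 at Θ = 0.10 need no change.

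Separately, the sponsor should decide and state what a single related death triggers for accrual, because this edit does not settle that.

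The cost is a short amendment. No new data are needed, since Grade 5 events are already collected and expedited. The price is a higher chance of a hold if deaths occur: small if they are rare, and larger at the upper end of the range shown. Any such extra holds would reflect severe toxicity above the 10% that the rule is built around.
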